11 DATA ANALYSIS

Data collected throughout the study will be summarized using descriptive statistics and listed in by-subject listings. Continuous variables will be summarized using number of subjects with

data, mean, standard deviation, median, minimum, and maximum. For categorical variables, the number and percentage of subjects in each category will be tabulated. Summaries will be provided by treatment group within appropriate analysis populations (as defined in [Section 11.2, Study Analysis Populations](#)) and by time point/time period as appropriate.

For Hb, Baseline will be calculated as the average of the central laboratory Hb measurements of samples taken at the screening visit closest to the date of randomization and the measurement taken at randomization. For other parameters, unless otherwise specified, Baseline will be defined as the last available value prior to the first dose of study medication.

Hemoglobin values as assessed through the central laboratory will be used for efficacy and safety evaluations; local HemoCue Hb values will be used only for dose adjustments.

11.1 Sample Size Determination

The goal of this study is to demonstrate the efficacy and safety of vadadustat compared with darbepoetin alfa for the maintenance treatment of anemia in subjects with anemia secondary to NDD-CKD after conversion from current ESA therapy. The sample size is calculated to ensure sufficient power for testing both efficacy in this trial and the primary safety endpoints as part of a pooled analysis.

11.1.1 Sample Size for the Primary Efficacy Endpoint

The primary efficacy endpoint is defined as the mean change in Hb from Baseline (mean pretreatment Hb) to the average Hb over the primary evaluation period (mean Hb from Weeks 24-36).

The primary efficacy objective of this study is to show that vadadustat is noninferior to darbepoetin alfa within the noninferiority margin. Noninferiority will be established based on a margin of -0.75 g/dL (for vadadustat minus darbepoetin alfa).

For the primary efficacy analysis in this study, it is assumed that the mean change from Baseline in Hb for vadadustat will be the same as for darbepoetin alfa, and the common standard deviation for the mean change from Baseline is assumed to be 1.5 g/dL. Noninferiority will be established based on a 2-sided 95% confidence interval for the difference between the vadadustat group and darbepoetin alfa and using a noninferiority margin of -0.75 g/dL. With these assumptions and approximately 925 subjects per treatment group for the primary efficacy analysis, the noninferiority assessment will have > 90% power.

11.1.2 Sample Size for the Primary Safety Endpoint

The primary safety endpoint is the time from randomization date to the first (adjudicated) MACE +1.

The primary safety analysis will be based upon all events that accrue across the 2 NDD-CKD studies (Studies AKB-6548-CI-0014 and AKB-6548-CI-0015). The sample size with respect to the MACE endpoint has been determined based on the number of events needed to demonstrate noninferiority of the 2-sided 95% confidence interval for the hazard ratio (vadadustat/darbepoetin alfa). It has been calculated that 631 events will be required overall to have 80% power to establish noninferiority with a margin of 1.25, and >90% power to establish noninferiority with a margin of 1.3, assuming no difference between treatment groups. The

power is >90% to establish a noninferiority margin of 1.25 if the hazard ratio is 0.95 favoring vadadustat. A MACE rate of 10% annually is anticipated in both treatment arms based on a comprehensive review of available epidemiology and prospective clinical studies in the field. The number of MACE in each study will be a function of the actual pattern and size of enrollment as well as the duration of follow-up.

11.2 Study Analysis Populations

The following analysis populations will be used in this study:

- Randomized population: defined as all randomized subjects
- Full analysis population: defined as randomized subjects receiving 1 or more doses of study medication and had at least one Hb assessment during the primary efficacy evaluation period. This population will be analyzed based upon the randomized treatment.
- Per protocol (PP) population: defined as all randomized subjects who received study medication (vadadustat or darbepoetin alfa) during the primary evaluation period, had at least 2 Hb assessments during the primary evaluation period, received no rescue therapy (with ESA or RBC transfusion) in the 8 weeks prior to the evaluation period, and have no protocol deviations affecting the primary endpoint analyses. Protocol deviations leading to exclusion from the per protocol population will be specified prior to database lock on a blinded basis and recorded in a separate document.
- Safety population: defined as all subjects who received at least 1 dose of study medication. This population will be analyzed based upon the actual treatment received.

Efficacy analyses will utilize the randomized, full analysis, and PP populations while safety analyses (including MACE) will utilize the randomized population.

11.3 Analysis of Demographic and Pretreatment Variables

Descriptive statistics will be generated for demographic and pretreatment variables for each analysis population defined in Section 11.2, Study Analysis Populations.

Medical history terms will be coded using the Medical Dictionary for Regulatory Activities (MedDRA) and summarized by System Organ Class and Preferred Term for each treatment group based on the safety population.

11.4 Disposition of Subjects

The number and percentage of subjects randomized and included in each analysis population will be summarized by treatment and overall. Reasons for excluding subjects from the analysis populations will be presented in a by-subject listing.

The number of randomized subjects who completed each period of study medication treatment (maintenance and long-term treatment), discontinued from study medication early, and completed or discontinued from the study and reasons for discontinuation will be summarized by treatment group and overall.

11.5 Missing Data

Subjects who stop study medication treatment after randomization and prior to completion of the study should continue with planned study visits and assessments unless they withdraw consent for participation in the study. Similarly, subjects will continue with study medication and study procedures following the initiation of rescue therapy, with the exception that the subjects must discontinue taking study medication while receiving an ESA rescue therapy. Treatment with study medication should be resumed after an appropriate interval following the ESA rescue therapy as described in [Section 8.4.7, Rescue Therapy](#). Data will continue to be collected following initiation of the rescue therapy as per the study Schedule of Activities.

All data collected during the study, including at any point after the initiation of rescue therapy as well as after early discontinuation of study medication treatment, will be used for the primary analysis as well as main analyses of all efficacy endpoints. Sensitivity analyses will be performed to assess an impact of rescue therapy on study conclusions.

In the primary analysis of the primary efficacy endpoint, all available qualifying Hb measurements during the pretreatment period and during the primary evaluation period (Weeks 24-36) will be used to calculate an average Hb during each period respectively, for each subject. For any subject with no available Hb measurements during the primary evaluation period, multiple imputation will be used to impute a change from Baseline value (details are provided in the SAP). In an analogous manner, an average Hb will be calculated for the secondary evaluation period (Weeks 40-52) for each subject. Given the design of this study where the subjects will continue to be assessed after early study medication discontinuation, it is expected that there will be only a minimal amount of missing data and the primary analysis should not be substantially affected by the imputation.

All data pertaining to the MACE endpoint collected at any point during the study, both during study medication treatment and post study medication treatment discontinuation, and regardless of the rescue therapy, will be used for the primary analysis of the MACE endpoint and its individual components.

Unless stated otherwise in the SAP, missing data for all other secondary efficacy and safety endpoints will not be imputed and the analysis will be based on observed data. For certain responder-type binary endpoints, subjects with no available data will be classified into one of the categories as described in the relevant sections of the SAP

11.6 Efficacy Analyses

The primary efficacy endpoint as well as all key and other secondary endpoints will be summarized using descriptive statistics by treatment group, as well as by study visit and/or analysis period as appropriate. Mean values of Hb as well as selected other efficacy parameters will be plotted across study visits/periods by treatment group.

11.6.1 Analysis of Primary Efficacy Endpoint

The primary efficacy endpoint is defined as the mean Hb change from Baseline (mean pretreatment Hb) to the mean Hb from Weeks 24-36 (inclusive).

11.6.1.1 Primary Analysis of Primary Efficacy Endpoint

The primary analysis will use an analysis of covariance (ANCOVA) with multiple imputation, stratified by the randomization strata and using Baseline Hb as the covariate.

A 2-sided 95% confidence interval (CI) will be calculated for the difference between treatment groups (vadadustat minus darbepoetin alfa).

Noninferiority of vadadustat will be established if the lower limit of this CI is ≥ -0.75 g/dL.

The primary analysis will be performed using the randomized population and the assigned treatment as described in [Section 11.2, Study Analysis Populations](#). All data collected during the study for subjects included in the randomized population at the time of analysis, including data collected at any point after the initiation of rescue therapy as well as after early discontinuation of study medication treatment, will be used for the primary analysis. Missing data will be handled using multiple imputation methodology as described in the SAP.

11.6.1.2 Sensitivity Analyses of Primary Efficacy Endpoint

[figure not shown]
- The following sensitivity analyses will be conducted: Primary analysis will be repeated using the full analysis population.
- Primary analysis will be repeated using only subjects with available Hb data during the primary evaluation period, ie, excluding subjects with no available data during the primary evaluation period.
- Primary analysis will be repeated using the PP population with the actual treatment received.
- Primary analysis will be repeated with alternate approaches to imputation of missing data as described in the SAP.
- Primary analysis will be repeated with imputation of data which may have been affected by a subject's having received any form of rescue (transfusion of ESA). Details are provided in the SAP.

11.6.2 Secondary Efficacy Analyses

Secondary efficacy endpoints analyses will be performed using the randomized and full analysis populations and the assigned treatment as described in [Section 11.2, Study Analysis Populations](#). Analysis for the key secondary efficacy endpoints will be repeated using the PP population with the actual treatment received.

11.6.2.1 Key Secondary Efficacy Analyses

Mean change in Hb value between Baseline and the secondary evaluation period (Weeks 40-52) will be analyzed using the same methodology as specified for the primary efficacy endpoint. Sensitivity analyses similar to those of the primary efficacy endpoint will be performed and details will be provided in the SAP.

11.6.3 Subgroups

Analyses of the primary efficacy endpoint and key secondary efficacy endpoints will also be performed using the randomized and full analysis populations, using the assigned treatment, for subgroups based on the following:

- Hb stratification level
- NYHA CHF stratification level
- Due to use of different target Hb levels in the U.S. vs. non-US, the endpoints will also be analyzed for subsets based on the target Hb level:
 - the U.S. subset will be assessed due to the target Hb range being 10.0-11.0 g/dL in the U.S.
 - the combined EU and ROW (non-US) subset will be assessed since the target Hb range is 10.0-12.0 g/dL in these two Regions
- Geographic region (U.S., EU, ROW)
- Age
- Gender
- Race

11.7 Safety Analyses

All analyses of safety data will use the randomized population.

[figure not shown]
11.7.1 Analysis of MACE and Expanded MACE Components

The primary safety endpoint, time to the first adjudicated MACE, will be analyzed as [date of the first MACE minus the date of randomization +1]. A MACE is defined as all-cause mortality, non-fatal myocardial infarction, or non-fatal stroke. Subjects who have not experienced a MACE by study closure will be censored on the date of their last study assessment. The hazard ratio (vadadustat/darbepoetin alfa) and its 95% confidence interval will be obtained from a stratified Cox proportional hazards model. As this study has not been designed to provide a stand-alone assessment of MACE, this analysis will be considered a descriptive analysis. A similar analysis as described for the primary analysis of the MACE endpoint will be performed with censoring of subjects 4 weeks following discontinuation of study medication if they did not have a MACE prior to that time.

An additional analysis as described for the primary analysis of the MACE endpoint will be performed with censoring at time of chronic dialysis initiation for subjects who have progressed to chronic dialysis and who did not have a MACE prior to that time.

The following safety endpoints will also be summarized using time to event methods as for MACE:

- 1) Individual components (all-cause mortality, non-fatal myocardial infarction, non-fatal stroke) of MACE
- 2) Thromboembolic events (defined as arterial thrombosis, DVT, PE, or vascular access thrombosis)
- 3) Hospitalization for heart failure

- 4) Expanded MACE, defined as all-cause mortality, non-fatal myocardial infarction, non-fatal stroke, hospitalization for HF, or thromboembolic event

For these endpoints the incidence ("yes"/"no") of the endpoint will be presented for each treatment arm. Kaplan-Meier curves will be presented for each endpoint as the time of endpoint free survival (ie, time until endpoint or death).

The primary MACE analysis will be based upon all events that accrue over the 2 NDD-CKD studies (Studies AKB-6548-CI-0014 and AKB-6548-CI-0015) (see [Section 11.1.2, Sample Size for the Primary Safety Endpoint](#)).

The SAP for this pooled MACE assessment in NDD-CKD subjects provides details of the primary analyses for MACE, for individual components of MACE, and for an expanded version of MACE. Details of sensitivity analyses and subgroup analyses are also provided in the MACE SAP.

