
Statistical Considerations
	
Primary Efficacy Endpoint Analysis
 
The primary efficacy endpoint is defined as the mean Hb change from Baseline (mean pretreatment Hb) to the mean Hb from Weeks 24-36 (inclusive).
 
The primary analysis will use an analysis of covariance (ANCOVA) with multiple imputation, stratified by the randomization strata and using Baseline Hb as the covariate.
 
A 2-sided, 95% confidence interval will be calculated for the difference between the vadadustat group and control group. Noninferiority of vadadustat will be established if the lower limit of this confidence interval is ≥ -0.75 g/dL.
 
Analysis of MACE and Expanded MACE Components
 
The MACE endpoint (adjudicated result) will be analyzed as the time (days) from randomization date to first MACE +1. Subjects who have not experienced an adjudicated MACE by study closure will be censored as of their last assessment time.
 
Major adverse cardiovascular events will be analyzed using a stratified Cox proportional hazards model with a model containing treatment group. The randomization strata will be used in this analysis. The primary MACE analysis will take place at study conclusion and will be based upon all subjects in the randomized population. The hazard ratio (vadadustat/control) will be estimated, together with its 95% confidence interval. As this individual study has not been powered to provide a stand alone assessment of MACE, this interval will be considered as descriptive. The time to first MACE will also be graphically presented using Kaplan-Meier curves.
 
These analyses will be repeated with censoring occurring 4 weeks following early discontinuation of study medication.
 
The following safety endpoints will also be summarized using time to event methods as for MACE:
 
 1) Individual components (all-cause mortality, non-fatal myocardial infarction, non-fatal stroke) of MACE 2) Thromboembolic events (defined as arterial thrombosis, DVT, PE, or vascular access thrombosis) 3) Hospitalization for heart failure 4) Expanded MACE, defined as all-cause mortality, non-fatal myocardial infarction, non-fatal stroke, hospitalization for HF, or thromboembolic event 
For these endpoints the incidence ("yes"/"no") of the endpoint will be presented for each treatment arm. Kaplan-Meier curves will be presented for each endpoint as the time of endpoint free survival (ie, time until endpoint or death).
 
An independent statistical analysis center will perform analyses in support of the Independent Data Monitoring Committee (IDMC).

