9 STUDY PROCEDURES AND SCHEDULE OF ACTIVITIES

Please see [Appendix A: Schedule of Activities](#) for a detailed table of the Schedule of Activities.

This study includes the following visits:

- Optional Pre-Screening
- Two Screening visits (SV1 and SV2)
- Baseline/Randomization visit (Week 0/Day 1)
- Year 1 Treatment Period Study Visits/Evaluations while receiving study medication: Weeks 2, 4, 6, 8, 10, 12 (± 3 days), and every 4 weeks thereafter until Week 52 (± 5 days)
- Year 2 Treatment Period Study Visits/Evaluations while receiving study medication: Weeks 64, 76, 88, and 104 (± 10 days)
- Year 3 Treatment Period Study Visits/Evaluations while receiving study medication: Weeks 116, 128, 140, and 156 (± 10 days)
- Year 4 Treatment Period Study Visits/Evaluations while receiving study medication: Weeks 168, 180, 192, and 208 (± 10 days)
- EOT visit (± 7 days)
- Follow-up visit: 4 weeks after the EOT (± 7 days).
- Unscheduled Visit(s)

The following sections describe the procedures to be completed during the study. Subjects are to be assessed by the same Investigator or investigative site personnel whenever possible.

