9.3.10 Follow-Up Visit

The Follow-up visit will be conducted in person or via the telephone 4 weeks after the EOT visit. The following activities/procedures will be performed:

- AE assessment
- RBC transfusions and ESA rescue
- Therapeutic phlebotomy
- MACE endpoint questionnaire.
- Recording of concomitant medications

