#### **3.2.2 Time to MACE Within 4 Weeks of End of Treatment**

Only a MACE that occurs up to and within 28 days inclusive after permanent discontinuation of study treatment (End of Treatment, EOT) will be included as a MACE Within 4 weeks of End of Treatment.

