#### 4.6 Analyses of Secondary and Other Cardiovascular Safety Outcomes

The following table summarize the cardiovascular safety outcomes related to MACE, the associated definitions, and the model that will be applied to each outcome.

| Adjudicated Outcome  | Definition of Outcome
First bullet: time to event for subjects with a MACE
Second bullet: time to censoring for subject who do not experience a MACE   | Model   |
|--|---|---|
| Time to MACE within 4 weeks of End of Treatment                | 
 
• Date of the first MACE occurring within 4 weeks of EOT – date of first dose +1
 
• Date of last study visit (including telephone contact) within 4 weeks of EOT where all the components of MACE were assessed – date first dose +1
 
          | Cox regression model with same stratification factors and covariates as primary MACE analysis   |
| Individual CEC-adjudicated components of MACE                  | The frequency of each MACE component (all-cause mortality, nonfatal myocardial infarction, and nonfatal stroke) will be shown. For each subject, the total number of these outcomes (i.e., total number of MACE) will be calculated, and descriptive statistics for total number of MACE will be shown. | Not applicable  |
| Time to components of adjudicated MACE                         | 
 
• Date of the first MACE components – date of first dose +1
 
• Date of last study visit (included telephone contact) when where all the components of MACE were assessed – date of first dose +1
 
  | Cox regression model or competing risk analysis with same stratification factors and covariates as primary MACE analysis                                      |
| Time to expanded MACE  | 
 
• Date of the first MACE (expanded definition) – date of first dose +1
 
• Date of last study visit (included telephone contact) when where all the components of MACE (expanded definition) were assessed – date of first dose +1
 
             | Cox regression model with same stratification factors and covariates as primary MACE analysis   |

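### The on-treatment MACE analysis counts events to day 28 after stopping but censors event-free subjects at their last contact inside that window, which biases its rate slightly upward

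*Protocol*

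**What the plan says.** **Censoring in the protocol.** Section 11.7.1 of Amendment 7-COL repeats the MACE analysis "with censoring of subjects 4 weeks following discontinuation of study medication if they did not have a MACE prior to that time". The synopsis agrees: "These analyses will be repeated with censoring occurring 4 weeks following early discontinuation of study medication".

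**Events in the MACE SAP.** Section 3.2.2 sets the event window: "Only a MACE that occurs up to and within 28 days inclusive after permanent discontinuation of study treatment" qualifies. The table in Section 4.6 takes the event date as the "Date of the first MACE occurring within 4 weeks of EOT". Neither place requires that a visit took place inside the window.

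**Censoring in the MACE SAP.** For subjects without an event, the same table in Section 4.6 uses the "Date of last study visit (including telephone contact) within 4 weeks of EOT where all the components of MACE were assessed".

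**Schedule.** Protocol Section 9 lists "Follow-up visit: 4 weeks after the EOT (± 7 days" and also "EOT visit (± 7 days". Section 9.3.10 sets the anchor: "The Follow-up visit will be conducted in person or via the telephone 4 weeks after the EOT visit". The Follow-up visit includes the MACE questionnaire.

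**The concern.** Events and follow-up time are collected under different rules. Take two subjects who stop on the same day and are both seen on day 30. The first had an MI on day 15, and it counts. The second had nothing, and the day-30 contact shows this for the whole window. That contact lies beyond 4 weeks, so the SAP rule sets it aside and censors the second subject at an earlier contact, normally the EOT visit.

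Person-time is therefore lost only from event-free subjects, and the on-treatment rate is pushed up. MACE SAP Section 4 plans events per person-year by treatment group for each type of event, so the bias reaches a reported number. It is not confined to early stoppers, because subjects still on drug at global study completion also have an EOT visit and then a Follow-up visit (Protocol 7.5.2). If the arms stop drug at different rates, the hazard ratio can also shift.

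**Working it through.** **1. The plan's own figure.** MACE SAP 2.5.1 asks for 631 events for 80% power at margin 1.25 with a true HR of 1. By Schoenfeld's formula with 1:1 allocation, events = 4(1.960 + 0.842)² / (ln 1.25)² = 31.4 / 0.0498 ≈ 631. It reproduces. It concerns the primary analysis and is not in dispute.

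**2. Share of Follow-up visits after day 28.** The window runs from day 21 to day 35 after the EOT visit, which is 15 days. The documents do not say how visits are distributed inside it, so these are assumptions:

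| Assumed visit pattern | Share after day 28 |
|---|---|
| Even over days 21-35 | 7/15 = 47% |
| Symmetric, 20% exactly on day 28 | (1 − 0.20)/2 = 40% |
| Symmetric, 40% exactly on day 28 | 30% |
| Symmetric, 60% exactly on day 28 | 20% |
| Even, EOT visit 0-7 days after the stop date, days counted from the stop | (7 + 3.5)/15 = 70% |

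**3. Post-EOT time credited to an event-free subject.** Assume even spread, the EOT visit on the stop date and no other contact in the window.
- SAP rule: (21 + 22 + … + 28)/15 = 196/15 = 13.1 days.
- Earlier of day 28 and the last full assessment: (196 + 7 × 28)/15 = 392/15 = 26.1 days. It is 28 days for anyone assessed again later.
- Protocol rule read literally: 28 days.

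The SAP rule loses the late share times 28 days. That is 13.1 days at 47% and 5.6 days at 20%.

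**4. Effect on the overall on-treatment rate.** Mean time before EOT is an assumption; 1.4 years (511 days) and 2 years (730.5 days) are shown. The event count is the same under both rules, so the rate ratio is the inverse ratio of person-time.
- 1.4 years: (511 + 26.1)/(511 + 13.1) = 1.025, or 1.028 against a flat 28 days.
- 2 years: (730.5 + 26.1)/(730.5 + 13.1) = 1.018, or 1.020 against a flat 28 days.
- 1.4 years with 60% of visits on day 28 and the rest even on both sides: credited time is 0.6 × 28 + 0.2 × 24 = 21.6 days, and (511 + 27.2)/(511 + 21.6) = 1.011.
- Extreme case, every EOT visit 7 days after the stop: credited time is (14 × 7 + 28)/15 = 8.4 days, and (511 + 28)/(511 + 8.4) = 1.038.

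**5. Effect on the hazard ratio.** A simulated Cox model was run with 1850 per arm, 200 replicates per scenario, follow-up of 365 to 1095 days, on-drug MACE at 8% per year and even visit spread. Both rules were applied to the same simulated data, and the comparison rule censors at exactly day 28. Stopping rates and post-stop event rates are assumptions.

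| Stopping per year, vadadustat vs darbepoetin | MACE per year after stopping | HR, SAP rule | HR, day 28 | Difference |
|---|---|---|---|---|
| 25% vs 25% | 8% | 0.9994 | 0.9995 | −0.0001 |
| 25% vs 25% | 50% | 0.9985 | 0.9985 | 0 |
| 35% vs 20% | 8% | 1.0117 | 1.0057 | +0.006 |
| 35% vs 20% | 50% | 1.0409 | 1.0350 | +0.006 |
| 50% vs 20% | 50% | 1.0917 | 1.0794 | +0.012 |

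In the first scenario the overall rate rose from 0.0796 to 0.0816 per year, a ratio of 1.025, in line with step 4.

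**The case against.** **Other contacts may fall in the window.** The SAP accepts telephone contacts. Protocol 11.5 asks subjects who stop drug to keep attending, Year 1 visits are every 2 to 4 weeks, and unscheduled visits include the MACE questionnaire (9.3.11). This stands as a limit on size: 13.1 days is close to a worst case for Year 1 stoppers. It does not remove the problem, because Protocol 7.5.5.4 makes visits after discontinuation flexible and scheduled visits after Week 52 are at least 12 weeks apart.

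**The SAP may refine the protocol, and its rule resembles the primary one.** Protocol 11.7.1 leaves details of sensitivity analyses to the MACE SAP, and censoring at the last full assessment is also the primary rule (MACE SAP 4.4). The delegation is fair. The resemblance is incomplete, because the primary rule has no 28-day limit on which contacts count and so discards no late contact. The clause that the SAP overrides the protocol is in the general SAP; the MACE SAP as supplied has none.

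**The analysis is supportive.** It is neither the primary analysis nor in the hierarchical list of MACE SAP 4.5. This stands and keeps the point minor.

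**Stronger readings the documents do not support.** A reader might infer that half of Follow-up visits fall after day 28. The protocol gives only the window, and 47% needs an even spread. A reader might infer that MACE cluster around stopping and so penalise the arm with more stops. No passage says so, and the 50% rate above is an assumption. A reader might take this analysis as the safeguard against off-drug time masking harm, and so see the noninferiority conclusion as threatened. The documents assign it no such role, and the primary comparison does not use this rule.

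**Conclusion.** The mismatch is real and is in the current texts. Applied as written, MACE SAP 4.6 counts events through day 28 but drops part of the same period for event-free subjects, which inflates the on-treatment MACE rate whenever a Follow-up visit falls after day 28 with no full assessment shortly before it.

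The effect is small. With evenly spread visits, no other in-window contact and 1.4 to 2 years of mean follow-up, the overall rate is about 2-3% too high. It is nearer 1% if most visits fall on the target day, and less again with telephone or unscheduled contacts. An EOT visit that trails the last dose pushes it up. The HR is unchanged with equal stopping and moves by about 0.006-0.012 under the assumed unequal stopping; the direction depends on which arm stops more. This is a minor correction to a supportive analysis.

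**What to change.** In the MACE SAP 4.6 table, replace the censoring bullet for MACE within 4 weeks of End of Treatment with: *the earlier of (a) EOT + 28 days and (b) the date of the last contact, whenever it took place, at which every MACE component was checked; minus date of first dose + 1*. State that EOT here means the date of permanent discontinuation, as in Section 3.2.2, and not the EOT visit, which has its own ±7-day window.

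A visit on days 29-35 then supports event-free status to day 28. A subject lost before day 28 is not credited with unobserved time, as a literal reading of the protocol rule would do. Because this differs slightly from the protocol wording (26.1 against 28 days when the Follow-up visit is the last contact), align Protocol 11.7.1 and the synopsis with it.

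Cost: one SAP sentence, one line of derivation code and a matching wording change in the protocol. No new data are needed.
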